8.3 Arm C

Procedures	Screening ⁱ (-4 weeks)	On Treatment				Follow-up ⁱⁱ		
		Salvage Therapy		Response Assessment ⁱⁱⁱ (45 days \pm 5 days after last day of RT)	Adjuvant Radiotherapy ⁴ (4 months after completion of salvage therapy)	Year 1	Year 2-3	
		Surgery	Radiation			(Q3M \pm 2 weeks)	(Q3M \pm 1 month)	
Informed Consent	X							
Medical History ^{iv}	X							
Eligibility Criteria	X							
Clinical Assessments								
Vital Signs, Weight ^v	X			X		X	X	
Physical Exam	X			X		X	X	
ECOG Performance Status	X			X		X	X	
Adverse Event Collection ^{vi}		At each visit						
Concomitant Medication Collection	X	At each visit						
Laboratory Studies								
Hematology ^{vii}	X							
Chemistry ^{viii}	X							
LDH	X							
PSA ^{ix}	X			X		X	X	
Disease Assessments								
Molecular imaging (e.g., fluciclovine PET/CT or PSMA PET/CT scan or other per PI discretion) ^x	X							
CT Scans						X ^{xi}	X ^{xi}	
Nuclear Medicine Bone Scans (if clinically indicated)	X					X ^{xii}	X ^{xii}	
TRUS Biopsy ^{xiii}	X							
Intervention								
Oligometastasectomy		X						
Salvage Prostatectomy ^{xiv}		X						
Salvage Prostate Radiotherapy ^{xv}			X					

SBRT or Hypofractionated Bone Radiotherapy			X				
Nodal IMRT ^{xvi}					X		
Correlative Studies							
Optional Blood ^{xvii}	X	X			X ^{xviii}		
Optional Archival Tissue ^{xix}	X						
Optional Fresh Tissue ^{xx}	X	X					
Questionnaires							
PRO and QOL Questionnaires ^{xxi}	X			X		X	X
RTOG Toxicity Evaluation ^{xxii}				X		X	X

ⁱ All pre-study/screening procedures should be completed within 4 weeks of study enrollment - with the exception of laboratory tests which need to be completed within 2 weeks prior to study enrollment, and imaging assessments which must be completed within 90 days of enrollment.

ⁱⁱ Follow-up procedures will occur every 3 months for 3 years beginning from the last day of RT unless stated otherwise.

ⁱⁱⁱ The response assessment visit will take place 45 ± 5 days after completion of salvage therapy (surgery and/or radiation).

^{iv} To include Charlson Comorbidity Index (See Appendix E)

^v Vital signs include systolic/diastolic blood pressure, heart rate, respiration rate, pulse oximetry, and body temperature. Height will be captured at screening only.

^{vi} Adverse events will be assessed after treatment has begun and at each time a patient is seen in clinic or scheduled for correlative sample collections. Adverse events will be collected every three months for one year after treatment discontinuation.

^{vii} Hematology includes CBC with differential and platelets.

^{viii} Chemistry includes sodium, potassium, chloride, carbon dioxide or bicarbonate, blood urea nitrogen (BUN), creatinine, glucose, total protein, albumin, calcium, AST, ALT, alkaline phosphatase, total bilirubin.

^{ix} PSA progression must be confirmed according to PCWG3 criteria, after at least 1 week. See Section 10.2.1.

^x To be performed at screening (within 90 days prior to enrollment).

^{xi} CT scans of the chest/abdomen/pelvis scans recommended to be performed 6 months and 1 year after completion of ALL treatments (salvage and adjuvant therapy) (\pm 2 weeks), and annually for 2 additional years (\pm 1 month) in patients without evidence of disease progression, otherwise as clinically indicated.

^{xii} Nuclear medicine bone scans recommended to be performed 6 months and 1 year after completion of ALL treatments (salvage and adjuvant therapy) (\pm 2 weeks), and annually for 2 additional years (\pm 1 month) in patients without evidence of disease progression, otherwise as clinically indicated.

^{xiii} TRUS biopsy must be performed at screening (within 1 year prior to enrollment) only for subjects who have been previously treated with definitive prostate radiotherapy and have disease recurrence in the prostate evidenced by positive molecular imaging (e.g., fluciclovine PET/CT or PSMA PET/CT scan or other per PI discretion).

^{xiv} Only for subjects who have been previously treated with an incomplete course of definitive prostate radiotherapy and whose baseline TRUS biopsy is positive. Can be replaced with salvage prostatectomy at the discretion of the treating physician.

^{xv} Only for subjects who have been previously treated with an incomplete course of definitive prostate radiotherapy and whose baseline TRUS biopsy is positive. Can be replaced with salvage prostatectomy at the discretion of the treating physician.

^{xvi} Only required for subjects with a confirmed lack of PSA response (see section 6.2.3.2) following salvage therapy (see PCWG3 criteria in appendix)

^{xvii} Optional blood draws may be performed prior to starting salvage therapy, at the next standard of care follow up visit after completion of salvage therapy, and at the time of confirmed PSA progression or radiological progression. See Section 14.3 for details.

^{xviii} After completion of salvage treatment, optional blood will only be collected once at time of confirmed disease progression.

^{xix} Optional archival tissue may be collected at baseline for all subjects for whom it is available. Archival tissue slides should not be cut until requested from the Central Lab. Lack of archival tissue will not be exclusionary.

^{xx} Optional fresh tissue may be collected prior to starting salvage therapy during the TRUS biopsy (if performed) and at the time of oligometastasectomy or prostatectomy (if indicated and if available after SOC tissue collection). See Section 14.1 and 14.2 for details.

^{xxi} Quality of life (QOL) questionnaires (FACT-P and Expanded Prostate Cancer Index Composite EPIC-26) will be collected prior to starting salvage therapy, at the Response Assessment Visit, and at each follow-up visits. See Appendices C and D.

^{xxii}To be performed at the Response Assessment Visit and at each follow-up visits. See Appendix A

9 STUDY PROCEDURES

9.1 Screening Evaluations

- Informed Consent
- Review of medical history (including Charlson Comorbidity Index), baseline symptoms and medications
- Physical exam with ECOG Performance Status
- Vital signs with weight and height
- Laboratory assessments:
 - CBC with differential
 - CMP to include Albumin, Alkaline Phosphatase, Aspartate Aminotransferase, Alanine Aminotransferase, Total Bilirubin, Calcium, Carbon Dioxide, Creatinine, Chloride, Glucose, Potassium, Protein, Sodium, and Urea Nitrogen
 - Lactate Dehydrogenase (LDH)
 - PSA
- Molecular imaging (e.g., fluciclovine PET/CT or PSMA PET/CT scan or other per PI discretion)
- TRUS biopsy (and fresh tissue collection for correlative studies) only for patients who have received prior definitive prostate radiotherapy and have disease recurrence in the prostate evidenced by positive molecular imaging (e.g., fluciclovine PET/CT or PSMA PET/CT scan or other per PI discretion).
- Optional Blood and archival tissue for correlative studies. Archival tissue slides should not be cut until requested from the Central Lab (see Section 14 for details)
- Questionnaires (FACT-P and Expanded Prostate Cancer Index Composite (EPIC-26))
- Review of eligibility

- Technetium bone scan (optional)

9.2 On Treatment Evaluations

- Safety (as defined in Section 15.5, using CTCAE v5.0 and the Clavien-Dindo Classification) as well as concomitant medication and treatments must be assessed every time a patient is seen in clinic once treatment has begun. Optional blood and tissue for correlative studies may also be collected.

9.2.1 Salvage Therapy

- Oligometastasectomy for subjects with nodal metastases (Arms B or C, without or with bone metastases).
 - Subjects who have received a full course of definitive prostate radiotherapy and whose TRUS biopsy is positive at screening (or less than or equal to one year before enrollment) can undergo simultaneous salvage prostatectomy, or, if their initial dose of radiation was felt to be insufficient, complete a course of salvage prostate radiotherapy.
 - Some optional tissue resected during the procedures (oligometastasectomy and/or prostatectomy) may be collected for correlative research purposes if available after SOC tissue collection.
- SBRT (or hypofractionated RT) for subjects with bone metastases only (Arm A).
- For subjects with both nodal and bone metastases, surgery will take place on Day 1 and SBRT will follow once the subject has recovered from surgery. (Arm C)

9.2.2 Prior to Response Assessment

- Optional blood collection for correlative studies (see Section 14 for details) may be collected at the first standard of care follow-up visit after completing all salvage therapy. This can be collected any time after completion of salvage therapy but prior to the response assessment visit.

9.2.3 Response Evaluation & Adjuvant Treatment

To be completed 45 days after completion of salvage therapy:

- Physical exam with ECOG
- Vital signs with weight
- Evaluation of PSA response (with confirmation in case of PSA progression)
- Questionnaires (FACT-P and EPIC-26)
- RTOG toxicity evaluation (only required for patients who underwent radiotherapy)
- Optional blood for correlative studies (see Section 14 for details)

9.2.4 Adjuvant Therapy

To be initiated within 4 months in case of confirmed non-complete PSA response:

- Adjuvant radiotherapy course

- The exact treatment modality will be a function of previous treatments received by the subject. See Schema and Section 6.2.3 for details)

9.3 Follow-up Evaluations

The follow-up calendar will be based on the date of completion of all study treatments (salvage and adjuvant therapy as needed)

To be completed every 3 months for 3 years after completion of treatment (salvage ± adjuvant):

- Physical exam with ECOG
- Vital signs with weight
- Evaluation of PSA response (with confirmation in case of PSA progression)
- Safety assessments
- Concomitant medication and treatments
- Questionnaires (FACT-P and EPIC-26)
- RTOG toxicity evaluation (only required for patients who underwent radiotherapy)
- Optional blood for correlative studies
- Adverse event collection for long term safety, mandatory

To be completed every 6 months for 1 year after completion of treatment (salvage ± adjuvant) then yearly for years 2-3:

- CT scans and technetium bone scan (optional)

10 CRITERIA FOR EVALUATION OF ENDPOINTS

10.1 Primary Endpoint: PSA Response Rate

The PSA response rate is defined according to the PCWG3 criteria as the proportion of patients achieving a PSA decline $\geq 50\%$ at 6 months after completion of treatment (salvage ± adjuvant).

10.2 Secondary Endpoints

10.2.1 PSA Progression Free Survival

PSA measurements will take place every 3 months after completion of treatment (salvage ± adjuvant) for a total of 3 years.

The PSA PFS is defined as the time elapsed between completion of treatment (salvage ± adjuvant) and the first occurrence of confirmed PSA progression as assessed according to the PCWG3 criteria: a $\geq 25\%$ relative increase of ≥ 2 ng/mL above the baseline or nadir, which is confirmed by a second consecutive value recorded a minimum of 1 week later.

10.3 Time to Recurrence

CT scans and optional bone scans will take place every 6 months for the first year after completion of per-protocol directed therapy then annually thereafter for a total of 3 years.

The disease-free survival is defined as the time elapsed between study enrollment and first occurrence of confirmed radiographic disease progression as assessed according to the PCWG3 criteria (soft tissue by CT or MRI scans according to RECIST v1.1, bone metastasis by bone scan according to the PCWG3 criteria).

Soft tissue recurrence is defined by RECIST 1.1 as a $\geq 20\%$ increase and absolute ≥ 5 mm increase in the sum of diameters of target lesions (at most 5 lesions and 2 lesions per organ) OR the appearance of one or more new unequivocal lesions OR the unequivocal progression of existing non-target lesions. Soft tissue progression does not require confirmatory scans.

Bone progression is defined PCWG3 criteria as the appearance at any restaging scan of ≥ 2 new lesions which persist or increase at the confirmatory scan (to be performed ≥ 6 weeks later) OR, if ≥ 2 new lesions are observed at the first restaging scan, the appearance of ≥ 2 additional new lesions at the confirmatory scan (to be performed ≥ 6 weeks later).

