⁹ PSA progression must be confirmed according to PCWG3 criteria, after at least 1 week. See Section 10.2.1.

¹⁰ To be performed at screening (within 90 days prior to enrollment).

¹¹ CT scans of the chest/abdomen/pelvis scans recommended to be performed 6 months and 1 year after completion of ALL treatments (salvage and adjuvant therapy) (\pm 2 weeks), and annually for 2 additional years (\pm 1 month) in patients without evidence of disease progression, otherwise as clinically indicated.

¹² Nuclear medicine bone scans recommended to be performed 6 months and 1 year after completion of ALL treatments (salvage and adjuvant therapy) (\pm 2 weeks), and annually for 2 additional years (\pm 1 month) in patients without evidence of disease progression, otherwise as clinically indicated.

¹³ TRUS biopsy must be performed at screening (within 1 year prior to enrollment) only for subjects who have been previously treated with definitive prostate radiotherapy and have disease recurrence in the prostate evidenced by positive molecular imaging (e.g., fluciclovine PET/CT or PSMA PET/CT scan or other per PI discretion).

¹⁴ Optional blood draws may be performed prior to starting salvage therapy, at the next standard of care follow up visit after completion of salvage therapy, and at the time of confirmed PSA progression or radiological progression. See Section 14.3 for details.

¹⁵ After completion of salvage treatment, optional blood will only be collected once at time of confirmed disease progression.

¹⁶ Optional archival tissue may be collected at baseline for all subjects for whom it is available. Archival tissue slides should not be cut until requested from the Central Lab. Lack of archival tissue will not be exclusionary.

¹⁷ Optional fresh tissue may be collected prior to starting salvage therapy during the TRUS biopsy (if performed) and at the time of oligometastasectomy or prostatectomy (if indicated and if available after SOC tissue collection). See Section 14.1 and 14.2 for details.

¹⁸ Quality of life (QOL) questionnaires (FACT-P and Expanded Prostate Cancer Index Composite EPIC-26) will be collected prior to starting salvage therapy, at the Response Assessment Visit, and at each follow-up visits. See Appendices C and D.

¹⁹To be performed at the Response Assessment Visit and at each follow-up visits See Appendix A.

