Appendix F- Prostate Cancer Clinical Trials Working Group 3 (PCWG3)

The PCWG3 was created to more accurately assess bone lesions and to describe PSA based progression. PCWG3 rules were designed to be used in conjunction with radionuclide ($^{90}\text{m}\text{Tc}$) bone scintigraphy and therefore should be used for all bone response assessments. Only bone lesions seen on bone scans will be followed for assessment of response.

Bone Assessments

Baseline Assessment

All bone lesions may be recorded as non-target lesions only and the number of lesions should be noted.

Response Assessment

While on treatment, follow-up scans should be assessed for progressive disease (PD), progressive disease unconfirmed (P Du), no progressive disease (Non-PD), no evidence of disease (NED), or non-evaluable (NE).

Table 1: Bone response assessment categories

Bone Response	Definition
PD	2 new lesions, not flare, persistent
P Du	2 new lesions, but confirmation is required by the second scan. The temporary marker of PD should be updated to PD or non-PD upon subsequent scans. If P Du is determined on the last scan, sponsor should update to PD upon analysis.
Non-PD	At least 1 bone lesion present, but not enough to trigger PD.
NE	Status of bone lesions cannot be determined.
NED	No lesions are seen on bone scan (either none at baseline or all have resolved).

Rules of Progressive Disease

- 2+2 Rule: If 2 new lesions appear on the first scan after the initiation of treatment, the response is classified as P Du and another scan is performed ≥ 6 weeks.
 - If the next scans show at least 2 new bone lesions in addition to those seen in the prior scan, the prior scan is to be considered confirmed PD.
 - If the next scan does not show at least 2 additional new bone lesions the lesions seen on the prior scan are considered pre-existing lesions. The bone response on the prior scan is updated to non-PD and new lesions seen on the first scan are ignored.
- Once outside of the flare window (the first 12 weeks of treatment) the appearance of new lesions must be confirmed with a second scan ≥ 6 weeks after the first scan.
 - If ≥ 2 new lesions appear on a scan the scan will be classified as P Du until a second scan confirms lesion persistence.

- If lesions are persistent on the second scan, the prior response will be updated to PD.
- If the lesions disappeared on the second scan, the prior response is updated to non-PD.

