- If 1 new bone lesion is seen on one scan classifying the scan as non-PD, but the following scan shows an additional new lesion (2 new lesions total between subsequent scans) the second scan will be classified as PD.
- Diffuse skeletal tumor involvement may result in a superscan. In this case, distinguishing between individual new bone lesions may be impossible. If a superscan occurs after baseline, the response will be considered PD and no further confirmation scans are required.

PSA Progression

PSA should be monitored at the beginning of every cycle. Any rise in PSA during the first 12 weeks of treatment should be monitored but should not be deemed evidence of progression. Record the percent change from baseline at 12 weeks. After a decline from baseline: record time from start of therapy to first PSA increase that is $\geq 25\%$ and ≥ 2 ng/mL above the nadir, and which is confirmed by a second value ≥ 3 weeks later (i.e., a confirmed rising trend).

Nodal and Soft Tissue Progression

Nodal and soft tissue documentation, tracking, and determination of progression will follow RECIST 1.1.

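### Section 10.3 and Appendix F give no single bone-progression rule for the first post-treatment scan: the same persistent lesions can be an event at month 6 or no event

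*Combined protocol and SAP*

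**What the plan says.** Section 10.3 defines bone progression by two clauses joined by OR. Clause 1 is "the appearance at any restaging scan of ≥ 2 new lesions which persist or increase at the confirmatory scan". Clause 2 is "if ≥ 2 new lesions are observed at the first restaging scan, the appearance of ≥ 2 additional new lesions at the confirmatory scan". Both place the confirmatory scan at least 6 weeks later.

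Appendix F has two rules that bear on a first post-treatment scan.

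- **2+2 rule.** The trigger is "If 2 new lesions appear on the first scan after the initiation of treatment, the response is classified as P Du" (unconfirmed progression), with no time limit. "If the next scan does not show at least 2 additional new bone lesions the lesions seen on the prior scan are considered pre-existing"; the earlier scan then becomes non-PD and its new lesions are ignored.
- **Outside-flare rule.** "Once outside of the flare window (the first 12 weeks of treatment) the appearance of new lesions must be confirmed with a second scan" at least 6 weeks later. If the lesions persist, the earlier scan becomes PD.

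The Arm A calendar (Section 8.1, footnote 12) has "Nuclear medicine bone scans recommended to be performed 6 months and 1 year after completion of ALL treatments", with a window of 2 weeks either side. The Arm B and C calendars carry the same footnote. Section 11.3 analyses time from enrollment to confirmed radiographic progression by Kaplan-Meier, for all evaluable subjects together and for each arm.

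**The concern.** A time-to-event endpoint needs one rule that turns a given set of scans into one event status and one date. For the first post-treatment bone scan the protocol supplies several rules, and they do not agree. Two assessors following the document faithfully could score the same subject as progressed at month 6 or as not progressed, with the lesions absorbed into the reference count.

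The trial is meant to provide a reference for later studies (Section 2), and it has 20 subjects split over three arms. A few records classified differently would visibly change a curve. Radiographic progression by PCWG3 or RECIST 1.1 is also an off-treatment criterion in Section 6.4.1, so the ambiguity reaches beyond the endpoint.

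**Working it through.** The plan states no figure on this point to reproduce. The check has three steps: timing, classification and an illustration of size.

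**1. Which Appendix F rule does the first scheduled scan meet?** Six months is 6 × 365.25 / 12 / 7 = 26.1 weeks. Less the 2-week window, the earliest scheduled scan is 24.1 weeks after treatment ends. The flare window is 12 weeks and runs from the start of treatment, so the scan is at least 24.1 − 12 = 12.1 weeks beyond it. The scan is also the first since treatment began. It meets both triggers.

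**2. Apply each rule to the same records.** A record is (new lesions at the first scan, how many of them persist, additional lesions at the confirmatory scan).

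| Record | 10.3 as written | 10.3, clause 2 alone | Appendix F 2+2 | Appendix F outside-flare |
|---|---|---|---|---|
| (2, 2, 0) | progression | none | none | progression |
| (2, 2, 1) | progression | none | none | progression |
| (3, 3, 0) | progression | none | none | progression |
| (3, 3, 1) | progression | none | none | progression |
| (2, 2, 2) | progression | progression | progression | progression |
| (2, 0, 0) | none | none | none | none |
| (2, 0, 2) | progression | progression | progression | none |

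The main conflict is in the first four rows: lesions that persist, with fewer than 2 additional ones. There 10.3 as written and the outside-flare rule give progression, and the 2+2 rule does not. Of the records tried, clause 2 of 10.3 adds an event to clause 1 only in the last row, where the first lesions vanish and two others appear. It is nearly redundant.

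**3. Illustration of size.** The documents give no bone-lesion rate, so these inputs are assumptions: new lesions follow a Poisson process at rate λ per month, all persist, and confirmation is at exactly 6 weeks (42 / 30.44 = 1.380 months). Every subject with 2 or more new lesions at the first scan then progresses under clause 1 of 10.3. Under 2+2 the subject progresses only if at least 2 more lesions arrive by confirmation. With m = 1.380 λ, that probability is 1 − e^(−m)(1 + m).

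| λ per month | m | Chance of 2 or more additional | Classified differently |
|---|---|---|---|
| 0.2 | 0.276 | 3.2% | 97% |
| 0.33 | 0.455 | 7.7% | 92% |
| 0.5 | 0.690 | 15.2% | 85% |
| 1.0 | 1.380 | 40.1% | 60% |

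The denominator is subjects with 2 or more new lesions at the first scan, not all 20 subjects. Confirmation later than 6 weeks leaves more time for additional lesions and shrinks the difference.

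**The case against.** The strongest reply is that the text can be read coherently. Appendix F may intend 2+2 for early scans and persistence after 12 weeks, in which case it agrees with clause 1 of 10.3 at month 6. Alternatively, clause 2 of 10.3 may be the specific rule for a first scan, in which case it matches 2+2. Each reading is possible, but neither is stated. The first needs a time limit that the 2+2 bullet lacks. The second needs clause 1 to exclude the first scan, which its wording does not do, and it still leaves 10.3 in conflict with the outside-flare rule at month 6.

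It is also fair that bone scans are optional or recommended, that the baseline bone scan is optional (Section 9.1), that a clinically indicated scan could fall inside 12 weeks, and that Section 11.3 calls all analyses exploratory. These points limit the effect but do not remove the contradiction.

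A reader might infer more than the documents support:

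- *Appendix F as a whole opposes 10.3.* It does not; its outside-flare rule agrees with clause 1.
- *Lesions accruing one at a time are progression without confirmation.* Appendix F says "2 new lesions total between subsequent scans) the second scan will be classified as PD", but this follows the general requirement to confirm new lesions, which may cover it. The absence of confirmation would be inferred from silence.
- *Bone events drive recurrence in Arms A and C, or a reset delays the event to month 12 at the earliest.* The first has no source, and a single new unequivocal soft-tissue lesion is an event without a confirmatory scan. The second overlooks scans done when clinically indicated.
- *The recurrence curve would be inflated by a known amount.* That needs lesion rates, scan uptake and a counting convention that the documents do not give.

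**Conclusion.** The point holds as an unresolved conflict between stated rules. For a first post-treatment scan at month 6 with 2 or more new lesions that persist, and fewer than 2 additional ones, clause 1 of 10.3 and Appendix F's outside-flare rule give progression. The 2+2 rule gives non-PD. That finding rests only on the wording and the scan calendar.

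The consequence is confined to bone events within one descriptive secondary endpoint and to the radiographic criterion in Section 6.4.1. The primary PSA endpoint and the sample size are untouched. The 60-97% range is an illustration under assumed rates, full persistence, confirmation at exactly 6 weeks and a bone scan being done; it is not an estimate for this trial. The documents do not settle which rule was intended. The correction is worth making because it is cheap and bears on event status and dates.

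**What to change.** Reconcile 10.3 and Appendix F into one bone rule for the endpoint. It should:

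- state which rule governs a first scan taken after the 12-week flare window;
- limit the 2+2 rule and clause 1 of 10.3 so that they cannot both apply to the same scan (deleting the word *any* from clause 1 would not do this, because the first scan would still be a restaging scan);
- state whether the event is dated at the first scan or the confirmatory scan;
- state whether new lesions are counted cumulatively from baseline;
- state whether lesions accruing one at a time need confirmation.

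Appendix F's flare-window wording supports using 2+2 only for a first scan inside the window, but the sponsor must confirm its intent. The radiographic-progression criterion in Section 6.4.1 should then be reconciled with the endpoint rule.

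The cost is a wording amendment. The confirmatory scan after 2 or more new lesions is already specified. Extra scans would arise only if confirmation is newly required for lesions that accrue singly.
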